1.0 SUMMARY

This is a prospective, randomized, longitudinal study of the clinical outcomes of osteoarthritis patients treated by two different alignment philosophies for total knee replacement. Participants will be treated using the Stryker Triathlon® Total Knee System for Total Knee Arthroplasty (TKA) implanted using either Stryker OtisMed® ShapeMatch® Technology (intervention) or Stryker PrecisioN v4.0 Knee Navigation (control). Health status and functional outcome measures will be recorded to quantify functional status of subjects before surgery and at each follow-up interval. An economics analysis will also be conducted to compare costs associated with each technology platform.

There will be 2 sites (North Shore Hospital, Auckland and Waitakere Hospital, Waitakere), 1 Principal Investigator and 6 co-Investigators for this study. A maximum of 50 cases will be enrolled in each group, for a total of 100 patients. It is expected that participants will be recruited over a 6 month period. Total duration of the study is expected to be 1.5 years.

The study consists of two groups:

- 1. Intervention Group: Treatment by total knee replacement with a target lower limb alignment determined using pre-operative imaging and kinematic alignment, implemented using Stryker OtisMed® ShapeMatch® Technology:
- 2. Control Group: Treatment by total knee replacement with a target lower limb alignment equal to neutral Mechanical Axis, implemented using Stryker Knee Navigation.

Pre-operatively, all participants will be required to undergo medical imaging assessment using Magnetic Resonance Imaging (MRI) of the affected lower limb. These images will then be used to manufacture the patient-specific cutting guides for preparation of the bones prior to implantation of the total knee replacement.

All participants (control and intervention groups) will be requested to attend visits preoperatively and post-operatively at 6 weeks, 6 months and 12 months. At these visits participants will complete assessments relating to quality of life, pain and functional outcome. In addition, participants will have standard knee X-rays taken preoperatively and post-operatively. A post-operative CT scan will be obtained for all participants in order to assess implant position and orientation.

All devices used in this study have been registered with MedSafe NZ and are approved for sale and use in New Zealand.

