This study will adhere to all relevant requirement and guidelines in relation to the conduct of clinical trials, including the Declaration of Helsinki (Appendix 5) and ICH Good Clinical Practice Guidelines, as implemented in New Zealand (Appendix 6).

An Extension Study will be undertaken to follow all patients (intervention and control group) who consent to continued follow-up. These patients will be followed out to 5 years post-surgery, with a follow up visit at 2 years and 5 years, to collect longer term data on radiographic and patient outcomes. Data will also be captured on the secondary objectives of revision rate, device-related adverse events and re-operation rates.

Visit Windows

Definition – Since it is not always possible for subjects to come in for a study visit on the exact date, most protocols allow a certain time period before or after the calendar date; this is known as the visit window. If a subject is not seen during the visit window, that visit will be regarded as a missed visit. Visit windows are calculated in reference to the baseline date, which is the surgery date (intra-op) for this study.

Patient Evaluation Schedule for All Patients

EVALUATION	History/ Pre-Op	Intra-Op	6 week	3 MO*	6МО	12MO
Demographics	√			-		
Medical History	✓					
MRI	√					
Surgical Details		√				
Oxford Knee Score	√		✓		√	✓
IKSS	✓		✓		✓	✓
FJS-12			✓		✓	√
WOMAC	√		✓		✓	√
EQ-5D-3L	✓		✓		✓	✓
VAS Pain	√		✓		✓	√
AP and ML X-rays	✓		✓			√
Perth CT Protocol				✓		

^{*3} month patient visit is non-standard, i.e. in addition to the usual follow-up routine for TKA patients.

The visit windows for this study are:

- Pre-Op = Within 2 months before the date of surgery
- Intra-op = Baseline time point
- 6 Weeks = +/- 2 weeks
- 3 Months = +/- 6 weeks (no patient visit CT scan only)
- 6 Months = +/- 1 month
- 12 Months = +/- 2 months

Extension Phase

EVALUATION	2 year	5 year
	follow-up	follow-up
Demographics	√	
Medical History	✓	
and Surgical		
Details Review		
Oxford Knee Score	1	✓
IKSS	1	✓
FJS-12	✓	/
WOMAC	✓	/
EQ-5D-3L	✓	✓
VAS Pain	√	/
AP and ML X-rays	✓	1
Long-leg weight- bearing x-rays	√	~

The visit windows for this study are:

- 2 years = +/- 6 months
- 5 years = +/- 6 months

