3.0 OBJECTIVES

The primary objective of this study is:

• To demonstrate, through calculation of Oxford Knee Score at 12 months postoperative, that total knee replacement (TKR) performed using the ShapeMatch® Cutting Guide provides improvement from preoperative levels of patient pain and function comparable to the improvement obtained with TKR performed using computer-assisted Navigation. Oxford Knee Scores will be calculated pre-operatively and at 6 weeks, 6 months and 12 months post-operatively.

The secondary objectives of this study are:

- The efficacy objective is to compare radiographic, pain, function and health-related quality of life (QOL) between the ShapeMatch® Cutting Guide group and the computer-assisted Navigation control group. This objective will be achieved by utilizing the following instruments pre-operatively and at the 6-week, 6-month and 12 month visits:
 - Perth CT protocol
 - AP and ML X-rays
 - Oxford Knee Score
 - The International Knee Society Score (IKSS)

- The Forgotten Joint Score (FJS-12)
- WOMAC
- EQ-5D-3L
- VAS Pain
- To compare the cost-effectiveness and cost-utility of the procedure between the ShapeMatch[®] Cutting Guide group and the computer-assisted Navigation control group. This objective will be assessed by recording and calculating the following parameters:
 - o Wound length
 - Total duration of operating procedure (anaesthetic time and skinto-skin incision time)
 - o Cost of consumable items used during operating procedure
 - Length of stay in hospital
 - o Quality-adjusted life-years (QALYs) from EQ-5D-3L

The hypothesis is that there is a statistically significant improvement in functional outcome 12 months following a primary Total Knee Replacement when kinematic limb alignment (using ShapeMatch® Cutting Guide) is used compared to that resulting from a goal of neutral mechanical axis alignment (using computer-assisted Navigation).

The Extension Study Primary Objective is:

To determine the clinical and radiographic outcomes at 2 years and 5 years post-surgery, in patients receiving a Stryker Triathlon[®] Total Knee System for Total Knee Arthroplasty (TKA) implanted using either Stryker OtisMed[®] ShapeMatch[®] Technology (intervention) or Stryker PrecisioN v4.0 Knee Navigation (control).

The Extension Study Secondary Objectives are:

 To determine the revision rate, device-related adverse events and reoperation rates.

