12.2 Data Capture and Analysis

All data will be recorded on 2-part NCR paper Case Report Forms (CRFs). The surgeon will complete and sign forms at the time of completion. Original CRFs will be collected by Stryker for data entry. Copies will remain at the Investigator site. Archiving will be undertaken in accordance with ICH/GCP guidelines (Appendix 6).

Any unclear or ambiguous data will be queried and all cleaned data will be entered into a database for tracking purposes.

The primary outcome data gathered from patients in each study group will be pooled and summarized.

For the primary objective of the study, the 95% confidence interval of the difference in total Oxford Knee Score improvement (at 12 months post-operative) between the Intervention Group and the Control Group will be computed. Two and five year data will be analysed as per the 12 month data.

For secondary objectives, independent two-sample t-test or Wilcoxon non-parametric rank-sum test will be used to compare the International Knee Society Score (IKSS), Forgotten Joint Score (FJS), WOMAC, EQ-5D and VAS Pain scores between the Intervention Group and the Control Group at all available visits. Please note that the test we intend on using will be dependent on the distribution of the data collected following appropriate normality testing. Adjustments will be made for multiple testing at each level.

Independent two-sample t-test or Wilcoxon non-parametric rank-sum test will also be used to compare cost-effectiveness and cost-utility between the Intervention Group and the Control Group. As mentioned above, this will also be dependent on the distribution of the data collected.

Adverse events will be tabulated separately and reviewed for any commonalities. Revision surgery data from the Extension Study will be compared to the revision rates reported in the National Joint Registry report at 2 years and 5 years. A cost benefit analysis will be undertaken with the use of data from the Australian Government Hospital Casemix Protocol Annual Report.

A formal interim analysis will take place following completion of the ShapeNZRCT-10 study (12 month visit). Additionally, formal interim analyses will take place following all participants' completion of the 2 year visit and again following completion of all participants' 5 year follow-up visits.

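### Section 12.2 tests four secondary scores between arms before surgery, where a difference can only be chance, and leaves the same pre-operative values unused as baseline at follow-up

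*Combined protocol and SAP*

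**What the plan says.** For the secondary objectives, Section 12.2 states that an "independent two-sample t-test or Wilcoxon non-parametric rank-sum test will be used to compare the International Knee Society Score (IKSS") and the FJS, WOMAC, EQ-5D and VAS Pain "scores between the Intervention Group and the Control Group at all available visits". The choice of test depends on normality testing. The paragraph ends: "Adjustments will be made for multiple testing at each level". It names no correction method and does not say whether a level is a visit, a score or the whole set.

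Three places make pre-op one of those visits:
- Section 1.0 says participants are "requested to attend visits preoperatively and post-operatively at 6 weeks, 6 months and 12 months".
- The visit windows in Section 1.0 include "Pre-Op = Within 2 months before the date of surgery".
- Section 3.0 says the secondary efficacy objective is met by "utilizing the following instruments pre-operatively and at the 6-week, 6-month and 12 month visits".

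The table headed "Patient Evaluation Schedule for All Patients" ticks IKSS, WOMAC, EQ-5D-3L and VAS Pain at pre-op. FJS-12 has no pre-op tick.

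For the primary outcome, Section 12.2 analyses improvement in Oxford Knee Score, so the pre-operative score enters as baseline. For the secondary scores it mentions neither change from baseline nor covariate adjustment.

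**The concern.** A test between randomised arms before treatment has a true null hypothesis by construction. A significant result would say nothing about alignment method, and the plan has no rule for handling one. If the multiplicity correction pools visits, these tests also tighten the threshold for the follow-up comparisons that do address the secondary objective.

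The pre-operative score is useful elsewhere. As a covariate it removes between-patient variation from the follow-up comparison and corrects for any chance imbalance. As written, the plan uses the value as a tested outcome and not as an adjustment. What is at stake is the precision of the secondary efficacy comparisons.

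**Working it through.** **Inputs.** From Section 12.1: difference 5 points (37 to 42), SD 8.30, significance level 5%, power 80%, 45 per group, 50 after allowing for loss to follow-up. From the schedule: four scores at pre-op, 6 weeks, 6 months and 12 months; FJS-12 at the last three; all five at 2 and 5 years. Assumed: Bonferroni, because no method is named; the Oxford standardised effect, because no effect size or SD is given for the secondary scores; and the pre/post correlations.

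**The plan's own figure.** n = 2(1.960 + 0.842)² × (8.30/5)² = 2 × 7.85 × 2.756 = 43.3, so 44 by the normal approximation. The exact two-sided t-test gives 44.2, so 45. The stated 45 reproduces. With d = 5/8.30 = 0.602 and 45 per group, noncentral-t power is 80.7%. All power figures below use the noncentral t.

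**Number of tests.** Main trial: 4 × 4 + 1 × 3 = 19, or 5 × 3 = 15 without pre-op. Adding 2 and 5 years (5 × 2 = 10) gives 29, or 25 without pre-op.

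**Chance of any false pre-op difference.** For four independent tests with family size m, this is 1 − (1 − 0.05/m)⁴.
- Family is the pre-op visit (m = 4), or one score across four visits (m = 4): 1 − 0.9875⁴ = 4.9%.
- All 19 tests: 1.0%.
- All 29 tests: 0.7%.

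**Follow-up power with and without the pre-op tests.**

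| Family | Tests with / without pre-op | Power with / without pre-op | Loss (points) |
|---|---|---|---|
| One visit | 5 / 5 | 59.0% / 59.0% | 0 |
| One score, main-trial visits | 4 / 3 | 62.1% / 66.2% | 4.1 |
| One score, with extension | 6 / 5 | 56.5% / 59.0% | 2.5 |
| All scores, main trial | 19 / 15 | 41.2% / 44.1% | 2.9 |
| All scores, with extension | 29 / 25 | 36.1% / 37.8% | 1.7 |

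The one-score rows do not apply to FJS-12, which has no pre-op test to remove.

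**Power from using the pre-op score as a covariate.** Adjustment multiplies the residual SD by √(1 − r²), so the effective effect is d/√(1 − r²).

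| r (assumed) | √(1 − r²) | Effective d | Power at 0.05 | Power at 0.01 (= 0.05/5) |
|---|---|---|---|---|
| none (as planned) | 1 | 0.602 | 80.7% | 59.0% |
| 0.3 | 0.954 | 0.632 | 84% | 64% |
| 0.5 | 0.866 | 0.696 | 90% | 75% |
| 0.7 | 0.714 | 0.844 | 98% | 91% |

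The gain over the planned test is about 3, 10 or 17 points at 0.05, and about 5, 16 or 32 points at 0.01. It does not depend on what a level means.

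**The case against.** The strongest reply is that little turns on the pre-op tests. The same paragraph promises a multiplicity adjustment, and no decision in the plan depends on a baseline test. The sentence on levels directly follows the one on visits, so a level may well be a visit; follow-up thresholds then do not move at all. Two-sample comparisons of randomised arms at each follow-up visit are valid without adjustment. All of this stands, and it limits the direct harm to what the working shows.

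A reader might still infer two stronger things.
- One is that the four pre-op tests carry an 18.5% chance of a spurious baseline difference (1 − 0.95⁴). That treats them as unadjusted 5% tests, contrary to the adjustment promised in Section 12.2.
- The other is that pre-op testing cuts power from 80.7% to 41% or 36%. Most of that fall comes from counting many follow-up tests in one family; removing pre-op recovers only 2.9 or 1.7 points of it. The 29-test family is also unlikely to govern the 12-month results, since Section 12.2 plans a formal analysis at 12 months, before the 2- and 5-year data exist.

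The reply does not justify the pre-op tests, and it does not address the unused baseline. Validity of the unadjusted comparison is not in dispute; the loss is of precision, using data the trial already collects.

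**Conclusion.** The point holds on the text. Pre-op is a visit, four of the five secondary scores are collected then, and nothing in the plan keeps them out of testing or uses them as baseline for the follow-up comparisons. FJS-12 is not affected.

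The pre-op tests themselves cost little: at most about a 5% chance of any false baseline difference, and 0 to about 4 points of follow-up power. The documents do not support saying that they exhaust the multiplicity correction. The larger cost is the power forgone by not adjusting for the pre-op score.

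These sizes assume Bonferroni, independent tests for the false-positive figures, the borrowed effect of 0.602, 45 evaluable patients per group, and correlations that the plan does not give. A weak pre/post correlation would make the gain small. The primary analysis already uses the pre-operative Oxford Knee Score as baseline and is unaffected.

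**What to change.** In Section 12.2:
1. Limit the between-arm tests of the secondary scores to the post-operative visits.
2. Show pre-operative IKSS, WOMAC, EQ-5D-3L and VAS Pain by group descriptively, without p-values.
3. Compare the arms at each post-operative visit with the pre-operative score as a covariate, by ANCOVA or a repeated-measures model. Compare FJS-12 unadjusted.

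The cost is wording and slightly different analysis code, with no new data or visits. Dropping the pre-op tests loses no information. The covariate uses one degree of freedom, which is negligible at 45 per group. The plan should say how a missing pre-operative score is handled, and what replaces the rank-sum test as the adjusted analysis when the distribution is clearly non-normal.

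Restricting formal testing to 12 months is optional and not part of this fix: it would turn the planned 6-week and 6-month tests into estimates only.

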12.0 STATISTICAL METHODS

12.1 Sample Size Justification

The New Zealand National Joint Registry reported a mean Oxford Knee Score of 37.05 (with a standard deviation of 8.30) at 6 months following total knee arthroplasty, using mostly conventional instruments (NZOA New Zealand Joint Registry, 2010). The registry also reports the following scoring categories: Excellent >41, Good 34-41, Fair 27-33, and Poor <27.

Kamat et al. (2009) undertook a study comparing the clinical outcomes of manual versus computer-assisted surgery instrumentations systems. A 5-point change in Oxford Knee Scores at a post-operative period of 6 months was determined to be a clinically meaningful difference.

A minimum of 45 patients per group are required, based on an improvement from 37 (mean Oxford Knee Score reported in the New Zealand registry) to 42 (scoring category of excellent), with 80% power and significance level of 5%.

An additional 5 patients per group (10%) has been included into the target patient number to allow for loss to follow-up, bringing the target to 50 patients per group.

A maximum of 100 patients will be enrolled in the Extension Study.

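### A normality test on the trial's own data decides whether five secondary scores and the costs are compared on means or on ranks, so the quantity compared is not fixed, and skewed costs would usually go to a rank test that cannot answer the cost objectives

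*Combined protocol and SAP*

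**What the plan says.** Section 12.2 (Data Capture and Analysis) treats three groups of outcomes differently.

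- **Primary outcome.** The plan computes "the 95% confidence interval of the difference in total Oxford Knee Score improvement (at 12 months post-operative") between the groups. No choice of test is involved.
- **Five secondary scores** (IKSS, FJS, WOMAC, EQ-5D, VAS Pain). These are compared by t-test or rank-sum test "between the Intervention Group and the Control Group at all available visits". The choice is governed by this sentence: "Please note that the test we intend on using will be dependent on the distribution of the data collected following appropriate normality testing".
- **Cost-effectiveness and cost-utility.** The same two tests are offered, and "As mentioned above, this will also be dependent on the distribution of the data collected".

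The section does not name the normality test or its cut-off. It does not say whether the test is applied per arm, pooled or per visit, and it states no effect measure for the secondary scores. On multiplicity it says only: "Adjustments will be made for multiple testing at each level".

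The schedules in Section 1.0 place these scores at 6 weeks, 6 months and 12 months, and at 2 and 5 years in the extension. All except FJS-12 are also scheduled pre-operatively. Section 3.0 lists consumable cost, operating time, length of stay and QALYs from the EQ-5D-3L among the inputs to the economic objective.

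**The concern.** The t-test compares means. The rank-sum test asks whether a patient in one arm tends to score higher than a patient in the other. These are different questions, and here the collected data choose between them. The same instrument could be compared on means at 6 weeks and on ranks at 12 months, leaving no common effect measure across visits.

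For costs the difficulty does not depend on error rates. A cost-effectiveness or cost-utility comparison needs the difference in average cost and average QALYs. Costs and length of stay are typically right-skewed, so a rule driven by distribution would tend to select the test that does not estimate that difference.

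There is also a question of level. If the result is read as a statement about means, a rank test can reject when the means are equal but the arms differ in shape or spread.

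**Working it through.** **1. The plan's own figure.** Section 12.1 gives SD 8.30, a change from 37 to 42, 80% power and a 5% level. With n = 2(z₀.₉₇₅ + z₀.₈₀)²σ²/δ² per arm:

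- δ = 5: 2 × 2.8016² × 68.89 / 25 = 43.3, so 44. The t-distribution version gives 44.2, so 45.
- δ = 42 − 37.05 = 4.95: 2 × 2.8016² × 68.89 / 24.50 = 44.1, so 45.
- Allowing 10% loss: 45 / 0.90 = 50.

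The stated 45 and 50 per group are reproduced. The simulations below use 45 per arm.

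**2. Assumptions.** The documents specify neither the normality test nor the score distributions. I took Shapiro-Wilk at 5% in each arm, with the t-test if both arms pass and rank-sum otherwise. There were 8,000 or 10,000 simulated trials per setting, and the Monte Carlo standard error at 10,000 is √(0.05 × 0.95 / 10,000) = 0.22 points.

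**3. How often the rule switches to ranks (same distribution in both arms).**

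| Distribution | Rank-sum chosen |
|---|---|
| Normal | 9.9% (expected 1 − 0.95² = 9.75%) |
| Beta(3,2), mild skew | 33% |
| Beta(4,2), skewness −0.47 | 52.4% (both arms pass in 47.6%) |
| Gamma, shape 4 | 86% |
| Beta(4,1) and exponential | 99.9% and 100% |

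In the Beta(4,2) case, three independent visits would all receive the same test with probability 0.476³ + 0.524³ = 0.25. Visits on the same patients are correlated, and with correlation 0.5 to 0.7 the figure is 32% to 36%.

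**4. Level when both arms share a distribution.** Rejection under the rule was 5.0% (normal), 5.0% (Beta(3,2)), 5.2% (gamma, shape 4), 4.8% (Beta(4,1)), 4.5% (exponential) and 5.5% (Beta(4,2), against 5.1% for the t-test). The level is essentially held.

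**5. Rejection when means are equal but spread or shape differs.**

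| Setting | Rule | Rank-sum alone | t-test |
|---|---|---|---|
| 100 × Beta(4,2) v Beta(2,1): mean 66.7, SD 17.8 v 23.6 | 7.1% | 6.8% | 5.0% |
| 100 × Beta(8,4) v Beta(2,1): mean 66.7, SD 13.1 v 23.6 | 10.7% | 10.1% | 5.2% |
| Beta(4,1) v Beta(8,2) | 9.6% | 9.6% | 5.0% |
| Gamma, shape 2 v 4 | 9.8% | 9.8% | 5.1% |
| Normal, SD 1 v 2 | 5.4% | 5.8% | 5.1% |

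Further runs in unequal-spread bounded-score settings gave 7.5% to 11.4% under the rule. Two deliberately extreme shapes (Beta(2,0.5) v Beta(8,2), and gamma shape 1 v 4) gave 31.0% and 31.8%. An unequal-variance (Welch) t-test gave 4.8% to 5.5% in all 11 settings where it was tabulated, covering same-distribution and equal-mean cases.

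**6. Where the excess comes from.** In the first two rows, the excess of the rule over the t-test is 7.1 − 5.0 = 2.1 and 10.7 − 5.2 = 5.5 points. The pre-test's own share is 7.1 − 6.8 = 0.3 and 10.7 − 10.1 = 0.6 points. A further run gave 8.8 − 8.2 = 0.6 and 10.6 − 9.9 = 0.7 points. The rest is the rank-sum test answering a different question.

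**7. Costs.** Take lognormal costs with equal means and log-SD 0.3 v 0.6. A lognormal median is the mean times exp(−σ²/2), so the medians are exp(−0.045) = 0.956 and exp(−0.18) = 0.835 of the common mean. The typical cost differs by 1 − 0.835/0.956 = 13% while the average cost is identical. The rule rejected in 25.8% to 26.7% of trials, against 6.1% to 6.6% for Welch, and it almost always chose ranks.

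**The case against.** The strongest reply is that the plan never states a mean-difference null for these scores. On that reading, a rank-sum rejection when the distributions really differ is a correct result under its own null. The 5% in Section 12.1 belongs to the primary sample size, and the secondary tests are to be adjusted for multiplicity, so no per-test 5% is promised. This stands, and it limits the level argument to readers who take the results as statements about means. Multiplicity adjustment, however, changes the threshold and not the quantity tested.

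A reader might infer that the 5% level fails generally. It does not: with a common distribution it is held. A reader might also infer that pre-testing causes the inflation. It contributes under one point; a Wilcoxon test fixed in advance would show nearly the same rates.

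The unequal-spread settings have no support in the documents. No SD or shape is given for any secondary score, and both arms receive the same prosthesis (Section 8.1). Different alignment targets make unequal spread possible, but it is not shown. Nor is the choice of test generally a coin flip: that holds for one assumed moderate skew, and for strongly skewed scores the choice is nearly deterministic.

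Finally, a rank test does not prevent means being reported or QALYs being calculated. That is true, but Section 12.2 commits to neither a mean difference nor an interval for these outcomes.

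**Conclusion.** The point holds in a limited form. For five secondary scores and the economic comparisons, the plan lets a distributional check on the collected data decide between means and ranks. The quantity compared can therefore change across outcomes and visits, and skewed costs would usually be compared on a scale that does not serve the economic objective in Section 3.0. The cost point is the firmest, because it rests on what the objective requires and not on simulated error rates.

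The level for a difference in means is not guaranteed when means are equal but spread or shape differs. It was about 7% to 11% for the main bounded-score settings and about 26% for one lognormal cost setting. These figures rest on 45 per arm, an assumed Shapiro-Wilk rule and assumed distributions, and are illustrative only.

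Two wider readings are not supported. The primary Oxford Knee Score interval and the sample size lie outside this rule. Nor are all secondary outcomes covered: Section 3.0 also lists the Perth CT protocol, X-rays and Oxford Knee Score, and Section 12.2 does not name them under it. The change is worth making, but the primary conclusion does not depend on it.

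**What to change.** Delete the normality-testing rule and pre-specify the following.

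- **Each of the five scores at every post-operative visit:** the difference in means with a 95% CI, from a linear model with unequal-variance (robust) standard errors. Adjust for the pre-operative value where the schedule collects it (IKSS, WOMAC, EQ-5D, VAS Pain; not FJS-12).
- **Rank-sum test:** a labelled sensitivity analysis, reported whatever the distribution looks like.
- **Costs and QALYs:** always the difference in arithmetic means, with a bootstrap CI.

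This also brings the secondary analyses into line with the primary one, which is already an estimated difference with a confidence interval. Baseline adjustment goes beyond what is needed to cure the switching, since an unadjusted Welch comparison would do that, but it uses data already being collected.

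The cost is a few sentences of analysis text and no new data. The downside is a small possible loss of power for very skewed scores, for which the rank-sum sensitivity analysis provides a check.

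### Section 12.2 names a t-test or rank-sum test for cost-effectiveness and cost-utility, but defines no total cost per patient, no cost-utility measure and no method for its uncertainty

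*Combined protocol and SAP*

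**What the plan says.** Section 3.0 sets the secondary objective of comparing the cost-effectiveness and cost-utility of the procedure between arms. It introduces a list with "This objective will be assessed by recording and calculating the following parameters" and names wound length, operating time, "Cost of consumable items used during operating procedure", length of stay and "Quality-adjusted life-years (QALYs) from EQ-5D-3L". Only the consumables are in money units. The schedule in Section 1.0 collects the EQ-5D-3L before surgery and at 6 weeks, 6 months and 12 months.

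Section 12.2 gives the method: "two-sample t-test or Wilcoxon non-parametric rank-sum test will also be used to compare cost-effectiveness and cost-utility" between the two groups, and "this will also be dependent on the distribution of the data collected". It adds, without a method, "A cost benefit analysis will be undertaken with the use of data from the Australian Government Hospital Casemix Protocol Annual Report".

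On platform costs, Section 1.0 says "An economics analysis will also be conducted to compare costs associated with each technology platform", and Section 11.0 promises parameters on each platform's effect on hospital cost and efficiency. Section 1.0 says of the MRI scans "These images will then be used to manufacture the patient-specific cutting guides"; Section 11.0 says controls are scanned to keep participants blinded. The listed appendices include no health-economic plan.

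**The concern.** Cost-utility is a joint comparison: the difference in mean cost set against the difference in mean QALY, with an interval that reflects how the two vary together within a patient. Section 12.2 names a test but not the quantity to be tested, and it plans no incremental cost per QALY and no interval. An analyst following it would have to invent the outcome after the data are in.

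The distribution rule adds a second difficulty. Costs are usually right-skewed, so the rule would tend to send them to the rank-sum test. That test asks whether patients in one arm tend to rank lower. A hospital budget and an incremental cost ratio both depend on the arithmetic mean, and the expensive few count fully in the mean but only by rank in the test.

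At stake is whether the trial can answer its own economic objective. The Oxford Knee Score analysis is not involved.

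**Working it through.** **Inputs.** The plan gives no cost, utility or price, so there is no economic figure to reproduce. The 50 per arm comes from Sections 4.0 and 12.1. Every cost and QALY value below is assumed, in arbitrary currency units.

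**1. What each possible reading of Section 12.2 delivers.**
- Testing the Section 3.0 items one at a time gives separate p-values, with no ratio and no joint uncertainty.
- Testing a per-patient cost/QALY ratio answers a different question. In an example with mean costs of 15,500 v 15,000 and QALYs around 0.75 v 0.72 (SD 0.15), the mean ratios were 21,659 and 21,929, a difference of about -270. The incremental cost per QALY in the same data was about +16,900, so even the sign differs.
- Testing per-patient net benefit by t-test would work, but the plan does not define net benefit or a threshold. A rank-sum test on it would again not compare means.

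**2. Why joint uncertainty matters.** For threshold L, cost SD sc, QALY SD sq and within-patient cost-QALY correlation rho,

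SE of incremental net benefit = sqrt[(2/n)(L²·sq² + sc² - 2·L·rho·sq·sc)].

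Take n = 50, sc = 3,000, sq = 0.10 and L = 30,000, so L·sq = 3,000 and 2/n = 0.04:
- rho = -0.5: sqrt(0.04 × 27,000,000) = 1,039; 95% half-width 1.96 × 1,039 = 2,037
- rho = 0: sqrt(0.04 × 18,000,000) = 849; half-width 1,663
- rho = +0.5: sqrt(0.04 × 9,000,000) = 600; half-width 1,176

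Widest to narrowest is 2,037/1,176 = 1.7. At L = 20,000 it is 1,709/1,037 = 1.6, and at L = 50,000 it is 2,744/1,709 = 1.6.

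With true differences of -1,000 in cost and +0.03 in QALY, net benefit at 30,000 is 30,000 × 0.03 + 1,000 = 1,900. In simulation (10,000 trials), separate t-tests reject in 37% to 38% of trials on cost and 32% on QALY at every rho. The net-benefit test favours the intervention in 44%, 60% and 88% for rho = -0.5, 0 and +0.5. The same component results therefore fit quite different joint conclusions.

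**3. Rank-sum on cost when true means are equal.** Base cost is normal with SD 2,000. A fraction of patients has a fixed amount added (the tail), and the base mean is lowered so that the overall mean is 15,000 in both arms. For a 12,000 tail the base mean is 15,000 - 0.10 × 12,000 = 13,800 with a 10% tail, 14,040 with 8% and 14,400 with 5%. With 50 per arm, 20,000 simulated trials and a nominal 2.5% per direction, the percentage calling the arm with more tail cheaper is:

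| Tail | Shares | Rank-sum | Welch t-test |
|---|---|---|---|
| 12,000 | 10% v 10% | 2.4 | 2.4 |
| 6,000 | 5% v 10% | 4.1 | 2.7 |
| 12,000 | 8% v 10% | 5.1 | 2.7 |
| 12,000 | 5% v 10% | 12.8 | 3.0 |

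Section 12.2 chooses the test after normality testing, so the 12,000-tail rows were rerun with an assumed Shapiro-Wilk step. The 8% v 10% and 5% v 10% results barely move, at about 5% and 12%. The extreme 0% v 10% case does move: it is about 40% if non-normality in either arm triggers the rank-sum test, and about 7% if both arms must be non-normal. The plan does not say which applies, so that case carries no weight here.

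**The case against.** The strongest reply is that the plan is silent rather than wrong. Section 12.2 does not say that the Section 3.0 items will be tested one by one. A t-test on per-patient net benefit would fit its sentence and would use the cost-QALY correlation. That is fair: a reader might infer that the plan has decided to ignore the correlation, and the documents do not support that. What stands is that the measure, the total cost and the uncertainty method are all undefined.

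On the rank-sum figures, the simulation forces equal means by lowering the base cost of the arm with more tail, so most patients in that arm really do cost less. The rank-sum test is answering its own question correctly. It is wrong only as an answer about mean cost, which is what an incremental ratio needs.

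On platform costs, a reader might infer that the MRI will cancel between arms, that navigation hardware will be left out, or that the guides will be entered free. No section says any of this. Sections 1.0 and 11.0 already call for a comparison by platform, under which an MRI done in controls only for blinding would naturally be excluded. Section 2.0 describes the comparator as the investigators' current standard of care, so counting navigation capital is a choice of perspective. Section 8.2 says who supplies the guides, not at what price, and single-use guides can be read as consumables. These are pricing details to clarify.

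The casemix sentence directly follows one about Extension Study revisions, so it may describe a separate analysis.

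**Conclusion.** The point holds for a secondary objective only. Section 3.0 promises a cost-utility comparison, and the tests in Section 12.2 do not deliver one, because the total cost per patient, the cost-utility measure and its uncertainty are undefined. This conclusion rests on the text alone.

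The sizes rest on assumed costs. If the distribution rule is applied to cost, true means are equal and tails are unequal, the rank-sum test misstates which arm is cheaper on average in about 5% or 12% of trials in the two middle cases, against 2.5%. With equal tails there is no inflation. Joint uncertainty can differ by a factor of 1.6 to 1.7 for the same component results, for correlations between -0.5 and +0.5. The documents give no data to say where in these ranges the trial would fall, and do not show that the economic result will be biased towards either arm. This is a cheap improvement to the analysis wording.

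**What to change.** Replace the economic-test sentence in Section 12.2 with: *Differences in arithmetic mean cost per patient and mean 12-month QALY (area under the EQ-5D-3L curve from pre-op, 6 weeks, 6 and 12 months, adjusted for pre-operative EQ-5D) will be estimated whatever the distribution. Incremental cost per QALY and incremental net benefit over a stated range of thresholds will be reported with confidence intervals from a bootstrap that resamples each patient's cost and QALY together within arm.* Define total cost per patient alongside it.

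As a clarification only, state in Section 3.0 that platform costs are charged as in routine use, with the blinding-only MRI not charged to the control arm. Give the guide price, say whether navigation capital is included, and vary these in a sensitivity analysis. Say whether the Australian casemix cost-benefit analysis is separate.

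The cost is more analyst work and some unit-price work. Results will depend on assumed prices, and intervals will be wide at 50 per arm. The EQ-5D-3L, operating time, consumables and length of stay are already planned. Re-operation costs may not be fully captured: Section 17.2 lists re-operation as a reason for leaving the study, Section 17.3 ends participation on unblinding, and the adverse-event form in Section 19.2 asks for treatment and dates but not cost. That should be stated as a limitation.
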